15.0 Risks to Subjects

This is a minimal risk study. All behavioral assessments and questionnaires have been used in research without any reported negative effects; rarely, participants experience mild temporary distress related to completion of behavioral measures. The adherence trackers (Propeller Health or FindAir) that will be provided to participants are registered with the FDA as a Class 1 Medical Device and therefore only pose minimal risk. Families also might be slightly inconvenienced by participating over a short period of time.

Several precautions will be taken to minimize the risk, discomforts, and inconveniences associated with this protocol. First, the PI is a licensed clinical psychologist and will oversee all study components. Thus, in the unlikely event of psychological distress resulting from questionnaires or assessment components, appropriate treatment and/or referrals can be easily made. All assessment components will be completed online or in conjunction with a pulmonary clinic appointment to lessen the burden of time and travel for families.

Knowledge gained in this study has the potential to improve treatment of pediatric asthma by enhancing disease management skills that, consequently, would improve treatment outcome in this population. The minimal risk posed to participants by this study is acceptable given that the knowledge that reasonably may be expected to result is substantial to the overall treatment of these patients and their families.

16.0 Potential Benefits to Subjects

Data from this project will inform clinical treatment of asthma through the empirical testing of an adherence-promotion intervention for adolescents with asthma. There is no guarantee of direct benefit to study participants. It is anticipated that at least some of the participants in this trial will benefit from the services provided. It is also anticipated that the pilot trial will provide important findings relative to the large-scale dissemination and implementation of the TASC intervention, ultimately benefitting additional patients with asthma.

Knowledge gained in this study has the potential to improve medication adherence in adolescents with asthma through the use of a technology-assisted empirically-supported behavioral intervention that is ready for dissemination. Despite existing adherence-promotion interventions for adolescents with asthma, nonadherence remains high and no technology-assisted interventions that can be easily disseminated are available. If this pilot trial is successful, there are pragmatic public health and clinical practice changes

PROTOCOL TITLE: Using Technology- Assisted Stepped Care Intervention to Improve Adherence in Adolescents with Asthma

that might emanate from this research. The study has the potential to advance existing adherence-promotion intervention science by shedding light on specific processes of change targeted by feedback and problem-solving based interventions. Our proposed examination of demographic factors may also help to explain why interventions work for some adolescents with asthma, but not others. The degree of risk to which study participants will be exposed in the proposed protocol is low. By contrast, the potential and probable benefits to be derived are substantial, insofar as the results will be used to enhance existing treatment or develop new interventions for this population. When considering the minimal risks entailed with participation and the extensive efforts proposed to limit/eliminate these risks, we feel that the potential benefits to the research community and future interventions far outweigh the potential minimal risks.

17.0 Data Management and Confidentiality

The primary outcome measure for Aim 1 at post-treatment is percent change in adherence to daily inhaled corticosteroids as measured by electronic monitoring devices compared to a treatment as usual control group. The secondary outcome measure is change in CASI scores. The expectation is that the TASC group will have an increased change in adherence and a decreased change on the CASI.

For Aim 2, the outcome measures are reach, acceptability, usability, and sustainability.

The exploratory outcome measures are clinical, demographic, and behavioral predictors of attendance, acceptance, and improvement in medication adherence and health within each intervention step.

Aim 1: To test the preliminary efficacy of the TASC adherence-promotion intervention for adolescents with asthma in a feasibility randomized controlled trial compared to treatment as usual control arm.

- Hypothesis 1 (H1): The TASC adherence-promotion intervention will result in improved adherence to daily inhaled corticosteroids as measured by electronic monitoring compared to a treatment as usual control arm.
- Hypothesis 2 (H2): The TASC adherence-promotion intervention will result in improved disease severity as measured by the Composite Asthma Severity Index combining symptoms, treatment, and exacerbations³⁰ compared to a treatment as usual control group.

The statistical test of choice for H1 and H2 will be an analysis of covariance (ANCOVA). Percent change in adherence is the primary clinical outcome of interest and change in CASI is the secondary outcome of interest. Seasonality will be controlled by recruitment of participants in waves and ensuring balanced enrollment across the study period. In the event that distributional assumptions are not amenable for analysis, nonparametric tests will be considered, as appropriate.

Aim 2: To assess the implementation of the TASC adherence-promotion intervention for adolescents with asthma through a process evaluation.

PROTOCOL TITLE: Using Technology- Assisted Stepped Care Intervention to Improve Adherence in Adolescents with Asthma

- Hypothesis 3 (H3): The TASC adherence-promotion intervention implementation will be successful as evidenced by high levels of acceptability, usability, reach, and sustainability.

For H3 acceptability, descriptive statistics of participant-reported and provider-reported satisfaction with intervention structure, length, convenience, and perceived impact on outcomes will be assessed⁸⁶. For usability, the statistical test of choice will be one-sample t-test tested at the nominal $\alpha_{2\text{-tailed}} = 0.05$ level. Usability will be evaluated using the SUS and a comparison score of 71 indicating good usability.⁸⁷ For reach, representativeness of the sample and enrollment rate of underserved individuals will be assessed. For sustainability, facilitators and barriers to delivering the intervention will be assessed.

Exploratory Aim: Examine clinical, demographic, and behavioral predictors of attendance, acceptance, and improvement in medication adherence and health within each intervention step.

Mediation and moderation of treatment effects will be examined using strategies outlined by Barron and Kenny⁸⁸, Holmbeck and colleagues^{89,90} using candidate covariates believed to be in the causal chain, including but not limited to, demographic characteristics, asthma symptoms, clinical presentation, treatment outcome expectancy (CEQ), and externalizing and internalizing problems (BASC).

A total of 60 participants will be needed for Hypothesis 1 analyses. Monte Carlo simulations in Mplus (version 8.1) were conducted to estimate statistical power assuming: 1) baseline adherence, asthma exacerbations, and race/ethnicity could explain between ($R^2 = 0.20-0.40$) 20%-40% of response variable noise variance, 2) participant attrition could range between 0%-20%, 3) alpha = .05, and 4) pre-post correlations similar to those reported in both the intervention literature and observed in our lab. The power analysis question involved identifying the smallest d effect size difference under these assumptions. Assuming proper handling of missing data, results showed power will be ≥ 0.80 for $d \geq 0.72$. Effect sizes larger than the one proposed have been documented in published studies^{12,91}, however, if statistical significance is not achieved, effect size estimates would inform design and power considerations for subsequent efficacy studies to further evaluate the TASC intervention. Up to 80 participants will be recruited to account for attrition.

Many procedures are in place to guard against missing or unusable data; however, missing data are almost inevitable in clinical research. The strategy for accommodating missing values is to first investigate and identify patterns of missingness, by group and variable, by using established pattern identification techniques. To the extent possible, potential mechanisms of missingness will be identified, including values deemed to be missing at random, completely at random, or not random at all. If substantial missing data are observed, parameter estimation using multiple imputation methods will be computed to estimate the missing values, and relevant predictors related to missingness will be added to our models. Sensitivity analyses will be conducted, with and without outliers/extreme values, and with and without imputed values to test the stability of our models under alternative conditions.

PROTOCOL TITLE: Using Technology- Assisted Stepped Care Intervention to Improve Adherence in Adolescents with Asthma

All data will be de-identified with the use of unique assigned study identifier codes. All electronic data will be stored on a CCHMC network server with built-in security. Treatsmart program data and web-based databases are located on a CCHMC secure server. Propeller Health or FindAir adherence data is located on their HIPAA-compliant servers and will be transferred securely to the CCHMC investigators at the end of the study for data analysis. Smartphones provided by CCHMC for use by the participants in the clinical study will be loaded with a security software program, Air Watch. Air Watch is a mobile device management technology that enables IT to deploy, configure, manage, support, and secure mobile devices from afar to provide remote configuration, troubleshooting, and lock and wipe security. Air Watch will not be loaded on participants' personal cell phones.

Propeller Health, FindAir, Treatsmart, asthma management app, and REDCap data will be stored on a secure, HIPAA compliant server and only approved study personnel will have access to the server (MAP) and data contained within the server. Informed consent/assent documents, and W-9 tax forms will be stored on a secure network drive with limited access. Any de-identified data will be confidentially protected with the use of unique assigned study identifier codes, and a master key linking identifying patient information (e.g., MR#) with the study ID code will be secured in a different locked file. The key, used for data entry purposes, will be destroyed as soon as possible after the completion of the study. Data will be retained until final data analyses are completed; all de-identified data will then be destroyed (e.g., shredded). Weekly audits to confirm access to database repositories and web application server environments will be conducted to ensure that it is limited to the appropriate user group. In addition, private conference rooms are available at CCHMC to ensure confidentiality during telehealth visits

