4.0 Study Endpoints

[figure not shown]
The primary study end point is post-treatment.

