feedback to obtain baseline adherence. If the participant did not bring their inhalers to the appointment, a coordinator will follow up with the patient to ensure that the Propeller or FindAir sensors are properly attached to the patients' inhalers. In addition, all participants receive a mobile spirometer (Spirobank Smart) to track their lung function throughout the study. The spirometer connects to an app (Propeller or FindAir) via Bluetooth. This app allows the participant to perform pulmonary function tests (PFTs) and view the results of these tests, such as their forced expiratory volume (FEV1) as well as other lung function parameters. Participants will be asked to use the spirometer at least once a month when completing study visits over the phone with a study team member. Following the baseline visit, a 8 week run-in phase will be completed to assess baseline adherence using electronic inhaler monitoring. After 4 weeks in baseline, the coordinator will call the participants in TASC and TAU for their first monthly phone call. After obtaining 8 weeks of baseline adherence data, the coordinator will call the participants in TASC and TAU for their second monthly phone call. The coordinator will calculate baseline adherence and obtain data for the Composite Asthma Severity Index (CASI) and the Asthma Control Test (ACT) for TASC and TAU participants. For TASC participants only, the coordinator will introduce Step 1 of the intervention for all participants. Adherence checks will continue to occur every four weeks for the duration of the study for all participants and adherence <68% will prompt movement from one level of treatment to the next for TASC participants only. The study coordinator will calculate the participant's adherence percentage prior to the monthly telephone call. During the call, the coordinator will tell the participant if they will get moved up to the next step and explain what they will be doing during that step. TASC participants may remain at a treatment level for more than four weeks and may complete 1, 2, or 3 interventions steps during the 5 month study depending on the adolescent's adherence.

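### The primary outcome, percent change in adherence, has no visible formula; if it means change relative to baseline, the planned ANCOVA loses power by an amount that depends on the unstated baseline spread

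*Combined protocol and SAP*

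**What the plan says.** Section 17.0 names the outcome twice, first as "The primary outcome measure for Aim 1 at post-treatment is percent change in adherence to daily inhaled corticosteroids as measured by electronic monitoring devices" and then again: "Percent change in adherence is the primary clinical outcome of interest and change in CASI is the secondary outcome of interest". On the method it says "The statistical test of choice for H1 and H2 will be an analysis of covariance (ANCOVA", and adds: "In the event that distributional assumptions are not amenable for analysis, nonparametric tests will be considered, as appropriate". The missing-data text in the same section promises sensitivity analyses with and without outliers or extreme values.

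Adherence is handled as a percentage throughout. In section 6.0 the coordinator works out each participant's "adherence percentage prior to the monthly telephone call". On timing, section 4.0 says only "The primary study end point is post-treatment". No visible text says which weeks supply that value.

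The power paragraph in section 17.0 assumes that "baseline adherence, asthma exacerbations, and race/ethnicity could explain between" 20% and 40% of the noise variance, refers to pre-post correlations without giving a number, and reports power of at least 0.80 for d of at least 0.72 with 60 participants. It adds that the effect-size estimate will inform later studies if H1 is not significant. Section 10.0 targets adolescents with a history of nonadherence and lists no minimum baseline adherence.

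**The concern.** For a variable already on a 0-100% scale, percent change has two ordinary meanings: post minus baseline in percentage points, or (post - baseline)/baseline. Read literally, it is the second, and that version behaves badly when denominators are small. A 20-point gain is +40% from a baseline of 50%, +400% from 5%, +1000% from 2%, and undefined from 0%. A trial that seeks out nonadherent adolescents may enrol some with small denominators.

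At stake is the test of H1, because the two versions can give different significance verdicts on the same data. The scale of the effect estimate that later studies are meant to use is also at stake. With neither version fixed in writing, the choice stays open until after the data are seen.

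**Working it through.** **1. The plan's own power figure.** Inputs from section 17.0: d = 0.72, alpha 0.05 (two-sided assumed), R² 0.20-0.40, attrition 0-20%, N = 60, equal arms. Power = Φ(d / √[(1 - R²)·2/n] - 1.96), with n per arm.
- Least favourable case, 48 analysed (n = 24), R² = 0.20: √(0.8 × 2/24) = 0.258; 0.72/0.258 = 2.79; Φ(0.83) = 0.796.
- A noncentral-t ANCOVA with three covariates gives 0.778 for that case. With 60 analysed it gives 0.865 (R² = 0.20) and 0.943 (R² = 0.40).

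The stated 0.80 reproduces to within about 2 points, provided d is on the scale of whatever variable is analysed.

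**2. Percentage points raise no problem.** If post = α + τ·arm + β·baseline + e, then post - baseline = α + τ·arm + (β - 1)·baseline + e. The treatment effect τ and its test are the same.

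**3. Why relative change differs.** Relative change is post/baseline - 1, so its residual SD at a given baseline is SD(e)/baseline. A participant at 10% has (50/10)² = 25 times the residual variance of one at 50%. Ordinary least squares weights them equally.

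**4. Size.** The documents give no mean, SD or correlation for adherence, so these are assumed: means 30/50/70%, SDs 10-25 points, pre-post correlation √R². Baseline and post values are correlated beta variables, counted in doses (112 at baseline, 56 at follow-up, assuming two a day). TASC adds 0.72 SD, clipped to 0-100%. A zero baseline is set to one dose. There are 2000 trials per scenario with N = 60. Each cell shows, for R² = 0.20, power for percentage-point change (equal to post-treatment adherence adjusted for baseline) / power for relative change / share of the relative-change residual sum of squares held by the six lowest baselines (equal share 10%).

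| Assumed SD | Mean 30% | Mean 50% | Mean 70% |
|---|---|---|---|
| 10 | 0.86 / 0.79 / 27% | 0.85 / 0.82 / 19% | 0.87 / 0.84 / 18% |
| 15 | 0.86 / 0.60 / 51% | 0.86 / 0.74 / 30% | 0.84 / 0.75 / 27% |
| 20 | 0.84 / 0.38 / 73% | 0.84 / 0.59 / 48% | 0.80 / 0.54 / 43% |
| 25 | 0.86 / 0.37 / 73% | 0.84 / 0.37 / 68% | 0.67 / 0.29 / 63% |

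At R² = 0.40 and SD 20-25, relative change gives 0.42-0.75 against 0.80-0.94. Relative change was lower in all 24 scenarios. At a mean of 70% with a wide spread, the ceiling at 100% lowers both. In a separate run that dropped zero baselines, mean 35%, SD 25 and correlation 0.45 gave 0.31 against 0.84. Mean 45%, SD 20 and correlation 0.45 gave 0.56 against 0.86, and the two analyses disagreed on p < 0.05 in 34% of trials.

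**5. Checks.**
- Cause: raising every baseline to at least 20% (mean 50%, SD 25, R² 0.20) restores relative-change power from 0.37 to 0.72 and cuts the share from 68% to 25%.
- No effect: relative-change ANCOVA rejects in 2.8-4.6% of trials.
- Rank ANCOVA of relative change keeps power of 0.61-0.98 over the 24 scenarios.
- Proportional instead of additive effect of the same mean size (means 35-55%, SDs 15-25): 0.57-0.88 for post-treatment adherence, 0.14-0.77 for least squares on relative change.

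**The case against.** The strongest reply is that percentage points were probably meant. Section 17.0 describes the expected change in adherence and in CASI in parallel terms, and a power simulation built on pre-post correlations with baseline adherence as a covariate fits levels or simple differences more naturally than ratios. A definition may also sit in the section 4.0 figure. This stands as far as it goes: the wording is compatible with percentage points, but it does not settle the matter.

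The plan also has safeguards. Nonparametric tests are a possible fallback, and a rank analysis would recover most of the loss under an additive effect. The analyses with and without extreme values bear directly on the problem. Both soften the point without removing it: no test, trigger or rule for extreme is given, and dropping extremes of relative change would tend to remove the least adherent participants, whom the trial targets.

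A reader might infer more than the documents support:
- That the trial is underpowered. The stated power reproduces on its own inputs, and the loss arises only if the 0.72 SD effect is in adherence while relative change is analysed by least squares.
- That false positives increase. They do not.
- That a few participants always dominate. That depends on a spread the documents do not give.
- That relative change conflicts with the rule that "adherence <68% will prompt movement from one level of treatment to the next for TASC participants only". That rule governs step-up in one arm and is not an outcome definition, so an outcome need not rank participants the same way.

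**Conclusion.** The missing formula is certain for the visible text. The loss of power is conditional on the relative reading, least-squares analysis and a wide baseline spread. For 60 participants and an additive effect of 0.72 SD of adherence, assumed SDs of 20-25 points with means of 30-50% give power of about 0.3-0.75 against 0.84-0.94, with the six lowest baselines holding 43-73% of the residual variance. At SD 10 with means of 50-70% the loss is about 2-4 points and the share about 20%; at a mean of 30% it is 3-7 points and 24-27%. If percentage points were meant, only the wording is at fault. It should be fixed because H1 rests on this variable, but it does not invalidate the design of a feasibility trial.

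**What to change.** In section 17.0:
- Define the primary analysis as ANCOVA on post-treatment adherence (percentage of prescribed doses taken) with arm, baseline adherence and the other covariates credited in the power paragraph (asthma exacerbations, race/ethnicity). Report the adjusted percentage-point difference with its 95% CI.
- State which weeks form the post-treatment value.
- State the baseline window as two months. Revision 3, the procedures text of section 6.0 and the appendix agree on this; the Electronic Monitoring item in section 6.0, which speaks of the first month, should be corrected to match.
- State the scale on which d = 0.72 was simulated.

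If relative change is kept instead, write its formula, name a baseline-adjusted rank test in advance and say how a zero baseline is handled.

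The cost is drafting only, since baseline adherence is already collected. If percentage points were meant, the treatment estimate does not change. If relative change was intended, moving to post-treatment adherence changes the primary outcome scale. It must be documented as such and made before the outcome data are analysed.

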18.0 Provisions to Monitor the Data to Ensure the Safety of Subjects

This study involves minimal risk to participants. Study personnel at CCHMC will monitor data collection, progress through treatment, any technical difficulties that may arise, adverse events, and completion of study procedures. Any adverse events (i.e., breach of confidentiality or events that are unexpected and related to the intervention) will be reported to the IRB within 48 hours. Participation will be discontinued at parent or patient request or if the investigators deem that it is in the best interest of the patient's health. The study team will provide referrals as appropriate for treatment needs resulting from any adverse events. The IRB requires yearly renewal of study protocols, which provides additional monitoring of participant safety. All other adverse events that happen in the course of the study procedures as well as minor deviations from protocol will be reported in table form at the next yearly continuing IRB review. The PI will review study data with her primary mentor at weekly meetings to ensure safety compliance and proper reporting to the IRB. In addition, the PI will have quarterly meetings with her mentorship team to monitor the progress of the study, the integrity of the treatment, discuss the need for any protocol refinements, and conduct regular safety monitoring checks of adverse

PROTOCOL TITLE: Using Technology- Assisted Stepped Care Intervention to Improve Adherence in Adolescents with Asthma

events. The PI will report any significant study related or unanticipated adverse events to not only the IRB, but also to the study sponsor based upon institutional and sponsor guidelines. Given that this pilot study is using evidence-based intervention, we believe that monitoring at the level of the PI, her mentors and research team, with oversight from the IRB and study sponsor is sufficient.

